#### 7.8.1.5 Adverse event of special interest (AESI)

##### Metabolic acidosis, ketoacidosis and diabetic ketoacidosis (DKA)

The frequency of patients with metabolic acidosis will be summarized by type and treatment group. Patients with DKA will be retrieved based on narrow BI-customised MedDRA query (BIcMQ) for DKA.

##### Decreased renal function/Hepatic injury

The frequency of patients with the protocol defined renal and hepatic events (See CTP, Section 5.3.6.1) will be summarised by primary SOC and PT as AESIs. The renal and hepatic events are identified through the AE being flagged as AESI on the eCRF.

AE frequency tables will also be created for renal and hepatic events based on narrow SMQs.

Renal: 20000003 Acute renal failure

Hepatic: 20000008 Liver related investigations, signs and symptoms (SMQ)  
20000009 Cholestasis and jaundice of hepatic origin (SMQ)  
20000010 Hepatitis, non-infectious (SMQ)  
20000013 Hepatic failure, fibrosis and cirrhosis and other liver damage-related conditions

##### Events involving lower limb amputation

The frequency of patients with events leading to lower limb amputation will be summarized by type and treatment group.

#### 7.8.1.6 Analysis of urinary tract infections (UTI) / genital infections

UTIs / genital infection will be tabulated based on the official BIcMQ.

The frequency of patients with UTIs / genital infections based on BIcMQ will be summarised by primary SOC and PT. The frequency tables by sex will also be provided for the UTIs / genital infections.

UTIs / genital infections will be summarised by intensity (mild, moderate, severe), age group, time of occurrence (in the first 3 months of treatment or after), time to onset of first event (0 to  $\leq 3$  months,  $> 3$  months), duration ( $< 7$  days, 7-14 days,  $> 14$  days), treatment for the event (no treatment, therapy assigned, hospitalisation), whether leading to discontinuation of treatment, and the number of episodes per patient.

Subgroup analyses of UTIs / genital infections with respect to age group, sex, baseline HbA1c, and history of UTI / genital infections will be performed.

In the analysis of the number of episodes of UTI and genital infection, AEs will be collapsed within each BIcMQ regardless of PT with the collapsing following the description at the start of [Section 7.8.1](#) but the condensing will not be conducted in order to maintain multiple episodes per patient.

Kaplan-Meier time to event analyses will also be presented for the UTIs and genital infections.

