3. DESCRIPTION OF DESIGN AND TRIAL POPULATION

3.1 OVERALL TRIAL DESIGN AND PLAN

This is a randomised, multi-centre, double-blind, and parallel groups study. The T2DM patients with insufficient glycaemic control despite treatment with liraglutide will receive either 10 mg or 25 mg of empagliflozin once daily as add-on therapy for 52 weeks.

In total, about 128 patients with T2DM are planned to be screened to ensure that 64 patients (32 patients for each treatment) are randamised in the double blind treatment period.

Patients who have signed the informed consent are enrolled in the study. Patients on liraglutide alone and suitable for the study after screening (Visit 1) undergo a 2-week openlabel placebo run-in period before randomisation. Patients treated with liraglutide plus one OAD and suitable for the study after screening (Visit 1) undergo a 10-weeks OAD washout period followed by the placebo run-in period before randomisation. Patients treated with one OAD alone and suitable for the study after screening undergo 14-week switch period (from OAD to liraglutide, including 2 to 4-week dose titration period) followed by the placebo run-in period before randomisation.

Patients who successfully complete the placebo run-in period and who still meet the inclusion but not meet the exclusion criteria will enter the 52-week double-blind treatment period of the study in which they will receive 10 mg or 25 mg of empagliflozin once daily. Randomisation of the treatment arms will be double-blinded and assigned at a ratio of 1:1 to one of 2 treatment arms shown in Figure 3.1:1. The patient participation is completed when they have undergone the last planned visit.

The end of the trial is defined as "last patient out", i.e. the last visit completed by the last patient.

The overall trial design is displayed in Figure 3.1: 1.

[figure not shown]

Figure 3.1: 1 Trial design

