4.1.4 Drug assignment and administration of doses for each patient

The treatments to be evaluated are outlined in Table 4.1.4: 1 below. Patients who are qualified will be randomised to one of the dosage and treatment schedules described below. Medication will be dispensed in a double-blind and double-dummy fashion.

All patients will be assigned to a placebo run-in kit at the beginning of the placebo run-in period (Visit 6), and dispensing will be done just once. Dispensing of kits for the double-blind treatment period will begin at Visit 7. Dispensing will be done on 8 occasions over a period of 52 weeks (i.e. every 4 weeks in Visit 7 to Visit 10; every 8 weeks in Visit 11 to Visit 14). Patients will receive empagliflozin as trial medication. However, background medication will not be dispensed as trial medication. Therefore, background medication (liraglutide) will be prescribed at each clinical site. For details regarding packaging (e.g. number of tablets per container), please see Section 4.1.6.

c03122586-03

Proprietary confidential information © 2017 Boehringer Ingelheim International GmbH or one or more of its affiliated companies

Table 4.1.4: 1 Empagliflozin, oral administration per dose group and day

Dose group	Empagliflozin	Empagliflozin	Total units	Timing
	10 mg	25 mg	per dose	
	C	S	1	
Placebo run-in period				
(open label)				
All patients	Matching placebo	Matching placebo	2 tablets	Once daily,
•				Morning
Treatment period				
Empagliflozin	Active drug	Matching placebo	2 tablets	Once daily,
10 mg	S	C 1		Morning
C	M. (1' 1 1	A - 4' 1	2 . 11 .	0 1.1-
Empagliflozin	Matching placebo	Active drug	2 tablets	Once daily,
25 mg				Morning

Placebo run-in period (open label):

From the start of the placebo run-in period, patients should be instructed to take their trial medication once daily with water. The medication should be taken at the same time every day. If a dose is missed by more than 12 hours, that dose should be skipped and the next dose should be taken as scheduled.

Double-blind period:

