For the analysis, all hypoglycaemias will be classified according to the following criteria:

- Asymptomatic hypoglycaemia: event not accompanied by typical symptoms of hypoglycaemia but with a measured glucose concentrations ≤70 mg/dL (3.9 mmol/L)
- Documented symptomatic hypoglycaemia with glucose concentrations ≥54 mg/dL and ≤70 mg/dL (≥3.0 mmol/L and ≤3.9 mmol/L): event accompanied by typical symptoms of hypoglycaemia
- Documented symptomatic hypoglycaemia with glucose concentrations <54 mg/dL (<3.0 mmol/L): event accompanied by typical symptoms of hypoglycaemia but no need for external assistance
- Severe hypoglycaemic episode: event requiring the assistance of another person to actively administer carbohydrate, glucagon or other resuscitative actions

Follow-up on suspicion for urinary tract infections

Patients having a history of chronic/recurrent urinary tract infections (UTIs) or genital tract infections (GTIs) or an acute episode of UTI or GTI at screening will be identified and this condition has to be documented as medical history or baseline condition in the eCRF, respectively.

For documentation of acute urinary tract infections during trial conduct, the following measures have to be taken:

- In any case of suspected UTI (symptomatic or asymptomatic) a urine culture sample has to be taken and sent to the central lab for confirmation of the diagnosis (including antibiogram).
- To be able to identify asymptomatic UTIs immediately, a dipstick-test (leukocyte esterase [for WBC] and Nitrite) will be performed at the site at each safety visit with urinalysis. In case of a positive result at site, a urine culture sample has to be taken and sent to the central lab for confirmation of the diagnosis (including antibiogram).

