#### 7.8.1.1 Assignment of AEs to treatment

The analysis of AEs will be based on the concept of treatment emergent AEs. That means that all AEs occurring between first drug intake till last drug intake + residual effect period (7 days for this trial) will be assigned to the randomised treatment. All AEs occurring before first drug intake will be assigned to ‘screening’ and all AEs occurring after the residual effect period will be assigned to ‘post-treatment’.

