#### 7.8.1.4 Analysis of hypoglycaemic events

The investigator will record for each AE whether it represents a hypoglycaemic event and, if so, record additional information to assess the intensity of the hypoglycaemic event as described in CTP, Section 5.3.3. On the basis of this information the hypoglycaemic event will be classified as:

- asymptomatic hypoglycaemia: event not accompanied by typical symptoms of hypoglycaemia but with a measured plasma glucose concentration  $\leq 3.9$  mmol/L (70 mg/dL),
- documented symptomatic hypoglycaemia with a measured plasma glucose concentration  $\geq 3.0$  mmol/L and  $\leq 3.9$  mmol/L ( $\geq 54$  mg/dL and  $\leq 70$  mg/dL): event accompanied by typical symptoms of hypoglycaemia,
- documented symptomatic hypoglycaemia with a measured plasma glucose concentration  $< 3.0$  mmol/L ( $< 54$  mg/dL): event accompanied by typical symptoms of hypoglycaemia but no need for external assistance,
- severe hypoglycaemic episode: event requiring the assistance of another person to actively administer carbohydrate, glucagon or other resuscitative actions.
- symptomatic hypoglycaemia and plasma glucose concentration  $> 3.9$  mmol/L (70 mg/dL)
- symptomatic hypoglycaemia and plasma glucose concentration not measured

The frequency of patients with hypoglycaemia according to investigator's judgement will be summarised by primary SOC and PT.

Confirmed hypoglycaemic AE is defined as hypoglycaemic AE with glucose value available and below 70 mg/dL or where assistance is required.

Summaries of confirmed hypoglycaemic AEs will include total number of hypoglycaemic AEs (asymptomatic and symptomatic), severity and intensity of the worst episode, action taken, minimum glucose level of worst episode, time to onset of first episode, and number of episodes per patient (asymptomatic and symptomatic).

Subgroup analyses of hypoglycaemic AEs with respect to age category, rescue therapy and renal function will be performed.

Summary table will include rate of confirmed hypoglycaemic AEs by severity, by age categories, and by renal function. For subgroup of age categories and renal function, time at risk for each group will be used.

Time to the onset of the first hypoglycaemia will be analysed by Kaplan-Meier estimates. The Kaplan-Meier analysis will be performed based on confirmed AEs.

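### SAP 7.8.1.6 splits UTIs and genital infections at 3 months without exposure adjustment, although the later period is about three times longer

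*SAP*

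**What the plan says.** SAP 7.8.1.6 lists the ways in which UTIs and genital infections will be summarised. Two of them cut follow-up at three months. One reads "time of occurrence (in the first 3 months of treatment or after" and places events by when they happened. The other begins "time to onset of first event (0 to" and sorts patients by whether their first event came by month 3 or later. The cut is not given in days, and no rate or person-time is specified.

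Two general rules then fix the form of the table. SAP 7.8.1 bases AE analyses on the number of patients with events. SAP 7 takes percentages over every patient in the set, whether or not the patient was still being followed.

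The same section keeps separate episodes within a patient for the analysis of episode numbers, and adds: "Kaplan-Meier time to event analyses will also be presented for the UTIs and genital infections".

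On follow-up, eligible patients "will enter the 52-week double-blind treatment period" (Protocol 3.1), and AEs count up to "last drug intake + residual effect period (7 days for this trial" days after the final dose, as SAP 7.8.1.1 sets out. On screening, Protocol 5.3.3 states: "To be able to identify asymptomatic UTIs immediately, a dipstick-test", to be done at each safety visit with urinalysis. The flow chart places on-treatment visits at weeks 4, 8 and 12 and then at weeks 20, 28, 36, 44 and 52, and its footnote 22 keeps the dipstick at the reduced-laboratory visits.

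**The concern.** The SAP does not say what the split is for, but a reader will use an early row and a late row to judge whether infections cluster after the start of treatment or continue through the year. The two rows cover very different amounts of follow-up, and nothing in the tabulation adjusts for that. A patient who stops in month 2 also stays in the denominator of the later row. A flat risk would look like late accumulation, and a moderate early cluster could look like no cluster. Both arms receive empagliflozin, so no placebo time course is available against which to read the pattern.

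Screening adds a smaller complication for UTI only: scheduled dipsticks become less frequent after week 12.

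**Working it through.** The plan gives no figure for this table. Its one design calculation supplies the dropout assumption used below. Protocol 7.7 needs 50 completers and allows about 20% dropout: 50 / 0.80 = 62.5, so 63, rounded up to 2 x 32 = 64. This reproduces.

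**Inputs**
- Treatment period: 52 weeks = 364 days (Protocol 3.1), or 371 days with the 7-day residual effect period (SAP 7.8.1.1).
- Cut: 3 months, taken as 91 days. Because the SAP does not define it, 84 to 92 days is the assumed range.
- Dropout: 20% over 364 days (Protocol 7.7), assumed exponential.
- Scheduled post-baseline dipsticks: days 28, 56 and 84, then 140, 196, 252, 308 and 364 after Visit 7 (flow chart).

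**Length of the periods**
- (364 - 91) / 91 = 273 / 91 = 3.00.
- Over cuts of 84 to 92 days and an end at day 364 or 371, the ratio runs from 2.96 to 3.42.

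**Person-time with dropout**
- Hazard of stopping: h = -ln(0.8) / 364 per day.
- Early days per patient: (1 - exp(-91h)) / h = 88.5.
- Late days per patient: (exp(-91h) - exp(-364h)) / h = 237.7.
- Ratio: 237.7 / 88.5 = 2.69.
- For 64 patients: 64 x 88.5 / 365.25 = 15.5 patient-years early and 64 x 237.7 / 365.25 = 41.7 late.

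**What the table would show**
- Take an illustrative constant rate of 10 per 100 patient-years (assumed). Expected events are 15.5 x 0.10 = 1.55 early and 41.7 x 0.10 = 4.17 late. Over 64 patients that is 2.4% against 6.5%, although the risk never changed.
- If the early rate is k times the late rate, the early count exceeds the late count only when 88.5k > 237.7, that is, k > 2.69.
- For first events only, with a 10% annual risk (assumed) and no dropout, 64 patients give about 1.7 early and 4.7 late, a ratio of 2.85.

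**Dipstick screening (asymptomatic UTI only)**
- 3 tests in 91 days against 5 in 273 days: (5/273) / (3/91) = 0.56. Over the same range of cuts and end days it is 0.49 to 0.56.
- The effect on detection depends on how long an episode stays detectable, which the documents do not give. Assume constant incidence from day 0 and detection at the first dipstick within the episode. Each test then picks up episodes that began within one episode length before it, or since the previous test if that is shorter.
  - 28 days or less: early/late detection rate (3/91) / (5/273) = 1.8.
  - 42 days: early tests capture 3 x 28 = 84 start days and late tests 5 x 42 = 210; (84/91) / (210/273) = 1.2.
  - 56 days or more: 84 against 5 x 56 = 280; (84/91) / (280/273) = 0.9.
- Visit 10 is planned for day 85 with a window of 7 days either way (days 78 to 92), so its dipstick can fall on either side of an undefined cut.

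**The case against.** The strongest reply is that the section already contains the right tool. Kaplan-Meier works with the patients at risk at each time, so it shows the time pattern of first events with period length and early stopping accounted for. That stands for first events. It does not reach recurrent episodes, which the section deliberately keeps, and it does not make the two tabulated rows comparable.

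Second, everything here is descriptive. No early-against-late test is planned, the row labels disclose the unequal periods, and both arms follow one schedule. That also stands: the comparison of 10 mg with 25 mg within a period is not biased by the split, and the primary endpoint does not use it. The denominator effect of early stopping is small as well: 1 - 0.8^(91/364) = 5.4%, or about 3 to 4 of 64 patients before day 91.

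Third, a reader might infer that the visit schedule determines the time pattern of both infection types. The documents do not support that. The dipstick looks for asymptomatic UTI; no scheduled dipstick screen for genital infection is described, and Protocol 5.3.3 has any suspected UTI cultured whenever it arises. A positive dipstick leads to a culture and is not in itself an adverse event. Length and screening also pull in opposite directions, the screening effect disappears for long episodes, and a strongly front-loaded risk would still show.

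Finally, SAP 7.8.1.4 says "For subgroup of age categories and renal function, time at risk for each group will be used", but this concerns rates by age and renal function, not periods of follow-up. It shows that time at risk is already part of this SAP; it is not an inconsistency with 7.8.1.6.

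**Conclusion.** The point holds as a modest defect of presentation. The two-period tables in SAP 7.8.1.6 carry no exposure adjustment. Under a constant risk they would show about 2.7 times more infections in the later row with 20% exponential dropout, and 3.0 times with none. An early rate up to about 2.7 times the later rate would not appear as an early excess. These figures rest on a 91-day cut and the assumed dropout pattern; without dropout, other readings of 3 months give length ratios of 2.96 to 3.42.

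Kaplan-Meier covers first events, so what is left uncorrected is the pair of tables themselves and the recurrent episodes. Reduced screening after week 12 may lower later detection of asymptomatic UTI, by an amount the documents do not allow one to fix. It warrants a footnote. It does not support the conclusion that the schedule produces the time pattern.

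**What to change.** In SAP 7.8.1.6:

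- Define the three-month cut in days.
- Report each period as patients, or episodes where episodes are counted, per 100 patient-years at risk within that period.
- Base the later row only on patients who, after the cut, are still on treatment or within the 7-day residual effect period, and show that number.
- For UTI only, add a footnote that scheduled dipsticks were at weeks 4, 8 and 12 and every 8 weeks afterwards (3 in 91 days against 5 in 273), so asymptomatic UTIs may be detected less often later. Person-time rates do not remove this effect.
- Separate asymptomatic from symptomatic UTIs only if the collected AE, central urinalysis or culture data allow it. This cannot be assumed: Protocol 5.3.3 says the site nitrite and leukocyte esterase results are not entered in the eCRF, and the AE items named in Protocol 5.3.7 include no symptom or trigger field for UTI.

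The cost is SAP wording, person-time from dosing dates already held, and one extra row per table. No new visits or data are needed for the rates. The drawback is imprecision: at the illustrative 10 per 100 patient-years, about 1.6 early and 4.2 late events are expected across both arms, so the rates should be shown with their event counts and patient-years.

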#### 7.8.1.7 Analysis of complicated UTI

Complicated UTI includes serious AEs of narrow BIcMQ UTI, all events of sub-BIcMQ pyelonephritis and all events of preferred term Urosepsis. Frequency of patients with complicated UTI will be summarized.

#### 7.8.1.8 Analysis of volume depletion

Volume depletion will be tabulated on the basis of the BIcMQ for overall summary and by age group and renal function based on baseline eGFR.

#### 7.8.1.9 Analysis of adjudicated events

Hepatic events will be adjudicated by an external expert committee. The patients with adjudicated hepatic events will be summarized by treatment and relationship with the trial medication.

## **7.8.2     Laboratory data**

The analyses of laboratory data will be descriptive in nature and will be based on BI standards (4). Baseline for safety laboratory parameters will be the last available measurement before the start of randomised study drug. Laboratory measurements taken up to 3 days after the last administration of randomised study drug will be considered as on-treatment. For continuous safety laboratory parameters, standardised and normalised values will be derived as well as the differences from baseline. The process of standardisation and normalisation as well as standard analyses for safety laboratory data is described in the BI guideline (4). All analyses considering multiple of times upper limit of normal (ULN) will be based on original and not normalised data.

